1. INTRODUCTION

1.1 BACKGROUND INFORMATION

Head and neck squamous cell carcinoma (HNSCC) accounts for more than 750,000 new cases per year (1) and its prognosis is still poor in terms of mortality and of morbidity and it causes approximately 350,000 deaths annually worldwide (2). The prognosis and therapy of this cancer are mainly related to the TNM stage and stage seems to be one of the most important prognostic features. Therefore, although advanced surgical techniques have increased the prognosis, it is still poor, with a survival rate which approximately varies between 25% and 45% in stages III and IV (3) (4) (5). Radiotherapy (RT) is an established treatment modality for HNSCC and other H&N tumors, either for treatment alone or as adjuvant (6) (7). Unfortunately, high-dose RT has significant adverse effects on the oral and maxillofacial tissues, both hard and soft, and dental management of these patients is based largely on individual and expert opinion, as few prospective studies have been performed to determine risk factors for adverse oral sequelae (8). In particular, when salivary glands are within the irradiated field, irreversible salivary glands damage occurs in 63–93% of the patients. Salivary gland damage typically manifests as reduced saliva secretion, which in turn can translate into a subjective sensation of dry mouth (xerostomia), oral discomfort, altered taste, difficulty with speaking, swallowing, chewing, and increased risk of dental disease. Overall hyposalivation and related xerostomia can cause a substantial reduction in quality-of-life (QoL). However there is currently little robust evidence to inform the management of hyposalivation and xerostomia in this population (9) (10). Although the treatment of xerostomia is very individual, a first-line medication is to ameliorate the dehydration in the mouth by substituting for the secretion of saliva. (11)

1.2 MEDICAL DEVICE DESCRIPTION

GUM Hydral (GUM Hydral: Sunstar Italiana SRL. [name]) is a product based on hyaluronic acid and sodium citrate. It helps in rehydrating and protecting the oral tissues, by forming a film on those tissues. It may be helpful in reducing the xerostomia symptoms.

1.3 FEATURES OF THE MEDICAL DEVICE

The device is a high-density liquid and it is used as a mouthwash. In this trial, the aim is to investigate if its efficacy in reducing the xerostomia symptoms is higher than placebo.

The placebo will be made of water with xylitol in addition. Xylitol is a sugar alcohol used as a sugar substitute, which does not increase the risk of tooth decay. In this formulation, its only role is to give a slight sweet flavor to water.

Water added with xylitol, in fact, may reduce, to a certain extent, the xerostomia symptoms, so it may be considered as a suitable comparator.

The device used for the clinical trial will be identified with visible marking stating “Exclusively for clinical investigations SSHNC-1 only”.

Funder will initiate the shipment of the medical device to the site upon the Principal Investigator received the Ethics Committee approval. Prior to any shipment, the site will be informed by the Funder/Sponsor on the upcoming shipment, expected arrival date and content of the shipment. The site should confirm receipt of the shipment.

Funder will also be encharged of the manufacturing and biological stabilization of placebo, whose composition is described above.

The placebo used for the clinical trial will be identified with visible marking stating “Exclusively for clinical investigations SSHNC-1 only”.

Funder will also initiate the shipment of the placebo to the site upon the Principal Investigator received the Ethics Committee approval. Prior to any shipment, the site will be informed by the Funder/Sponsor on the upcoming shipment, expected arrival date and content of the shipment. The site should confirm receipt of the shipment.

For the risk analysis please refer to the IfU (Instruction for Use).

1.4 PURPOSES AND OBJECTIVES OF THE CLINICAL TRIAL

The aim of this study is to describe the effect of the administration of Hydral on reducing patients' xerostomia symptoms due to radiotherapy. (12)

1.5 EXPERIMENTAL DESIGN

The study will be conducted as a double-blind randomized clinical trial (RCT) and foresees a crossover design, so the population will be divided into two groups, receiving both the medical device and the placebo. The interventions will be described in paragraph 2.3.

2 MATERIALS AND METHODS

2.1 PATIENTS SELECTION

Inclusion criteria:

- Patients willing to sign the informed consent form
- Patients older than 18 years
- Patients with diagnosis of HNC, who had received local radiotherapy at least three months before the beginning of the study, involving the salivary glands, both for curative and palliative purpose, with or without chemotherapeutic treatment, reporting xerostomia symptoms
- Patients with diagnosis of HNC, who had received local radiotherapy as an adjuvant to surgical resection at least three months before the beginning of the study, with or without chemotherapeutic treatment, reporting xerostomia symptoms-

Exclusion criteria:

- Patients with documented contraindication to any of the components of GUM HYDRAL (there included eccipients)
- Patients with any neurological and psychiatric condition having an influence on the ability to self-apply the treatment
- Patients unwilling to complete the request diary card
- Patients unable to attend the ambulatory visits scheduled by the protocol
- Patients participating to other clinical studies
- Patients who had received antitumoral treatment during the previous three months
- Patients with concomitant Sjogren's syndrome
- Other causes of xerostomia (pharmacological treatment)

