2.3 INTERVENTIONS

The patients will be recruited in the Oral Medicine Department, in a 12 months period.

Study design (see flow-chart)

A baseline visit (T_0) will be conducted three months after the end of RT.

The investigational product GUM Hydral and the placebo will be each administered for a 30-days treatment period.

The patients will be divided into two groups: at **day 1 (baseline - T_0)**, group A will receive treatment product, group B will receive a placebo.

At **day 15**, the compliance of the patient and any adverse effect will be evaluated by a phone call.

At **day 30**, the administration of the products will be stopped, and a 30 days washout phase will take part, followed by Phase 2 of the study.

At **day 61**, each group will be treated with the alternative product.

At **day 75**, the compliance of the patient and any adverse effect will be evaluated by a phone call.

At **day 90**, the final questionnaire will be administered, and the investigation of all endpoints will take place.

Each Visit is described in the following flow-chart

Activities/Procedures	Screening Visit (after 3 months from the end of the RT) From Day-3 to Day 0	Baseline Visit Day 1	DAY 15 (± 2 gg)	DAY 30 (± 7 gg)	DAY 31-60 Washout phase	DAY 61	DAY 75	DAY 90 (End of Study Visit) (± 7 gg)
	PHASE A					PHASE B		
Visit	V1	V2	V3	V4	V5 (Note 2)		V6	V7
Informed Consent signature	X							
Inclusion/Exclusion Criteria verification	X							
Randomization		X						
Demography	X							
Medical and surgical history and underlying diseases	X							
Previous and concomitant treatments	X	X		X	X	X		X
Physical examinations	X			X		X		X
Salivary flow measurement	X			X		X		X
Oral swab for mycetes determination	X					X		X
Medical Device administration and accountability (pts compliance to treatment is assessed at each protocol visit) (Note 3)		X (Note 4)	X	X		X (Note 5)	X	X
Diary card dispensing and verification		X	X	X		X	X	X
QoLs administration	X (Note 6)		X	X		X	X	X
AEs monitoring	X	X	X	X	X		X	X

Note1: the screening visit might have a maximum duration of 1 day

Note 2: during the washout period a telephone contact will be conducted, in order to assess the safety profile of the patients, by specifically asking to refer any AE occurred and relevant concomitant medications administered (if applicable)

Note 3: an instruction procedure to standardize the products administration will be finalized. Patients will be asked to rinse with 15 ml of product, three times a day.

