Note 4: PHASE A, Group A receives Hydral, Group B receives placebo

Note 5: PHASE B, Group A receives placebo, Group B receives Hydral

Note 6: this QoLS administration must be conducted after the ICF signature and before the first Medical Device administration

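### The contraindication exclusion in 2.1 covers GUM Hydral only, although the crossover schedules every patient for 30 days of placebo as well

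*Combined protocol and SAP*

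**What the plan says.** The only exclusion in section 2.1 that concerns tolerance of a study product reads "Patients with documented contraindication to any of the components of GUM HYDRAL (there included eccipients". It reaches excipients, but only those of the device.

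The trial uses two products, and each patient is meant to take both. Section 1.5 has the population "receiving both the medical device and the placebo". Section 2.3 adds: "The investigational product GUM Hydral and the placebo will be each administered for a 30-days treatment period". Under the flow-chart notes, Group B has placebo in Phase A and the groups then switch: "PHASE B, Group A receives placebo, Group B receives Hydral".

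On composition, section 1.2 says that Hydral "is a product based on hyaluronic acid and sodium citrate". For the comparator, section 1.3 states: "The placebo will be made of water with xylitol in addition". The same section makes the funder responsible for "manufacturing and biological stabilization of placebo, whose composition is described above".

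**The concern.** In a parallel-group trial, a criterion tied to the active product would leave the placebo arm unscreened. In a crossover, it leaves one of the two products given to every patient unscreened. A site that applies 2.1 as written has no criterion under which to exclude a patient whose records show a contraindication to something in the placebo but not in Hydral.

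What is at stake is an avoidable exposure of such a patient, repeated daily for a month. Two other provisions are drawn around the device in the same way. The stopping provision in 2.2 refers to adverse events attributable to GUM Hydral, and 1.3 refers the risk analysis to the Instructions for Use. Neither makes up for what the eligibility criterion omits.

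**Working it through.** The plan states no figure on this point, so the check sets the sections side by side.

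1. **Who is scheduled to take placebo.** By 1.5, 2.3 and the flow-chart notes, Group B takes it on days 1 to 30 and Group A on days 61 to 90. Each period is 30 days (30 − 1 + 1 = 30; 90 − 61 + 1 = 30). With the N = 40 of 2.8.1, placebo use is planned for 40 of 40 patients.

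2. **How much use that is.** Note 3 of the flow-chart gives three rinses a day and the Visit 1 description in 2.3.1 gives five. That is 3 × 30 = 90 or 5 × 30 = 150 placebo rinses per patient. The two frequencies contradict each other and must be reconciled. The present point holds under either.

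3. **Which criteria screen for it.** Section 2.1 has eight exclusion criteria. The first concerns Hydral. The other seven concern neurological or psychiatric conditions, the diary card, attendance at visits, other studies, recent antitumoral treatment, Sjögren's syndrome and other causes of xerostomia. None names the placebo, xylitol or hypersensitivity in general. The inclusion criteria do not either, and 2.1 has no clause for investigator discretion.

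4. **Whether the Hydral criterion covers the placebo indirectly.** It would if every placebo component were also a component or excipient of Hydral.
   - Section 1.2 names two ingredients on which Hydral is based. That is not a full list, and xylitol is not among them.
   - Section 1.3 names water and xylitol for the placebo.
   - No section says that Hydral contains xylitol, and none says that it does not.

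5. **Result.** There are two cases. If all placebo components are shared with Hydral, 2.1 already excludes the patients in question. If any is not shared, a patient with a documented contraindication to it passes 2.1. The documents do not settle which case applies, so a site cannot tell from the protocol whether its criterion is complete.

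**The case against.** The strongest reply is that the gap may be empty. The criterion expressly includes excipients, the full Hydral formula is not in the protocol, and xylitol may be one of its excipients. This stands as a limit. It would be too strong to infer that a patient with a xylitol contraindication is certainly eligible and will be exposed. Overlap is unknown, and exposure also requires that the patient is enrolled and reaches the placebo period, which for Group A begins only on day 61.

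A second reply concerns stabilization. A reader might infer from it that the placebo contains a preservative for which nobody is screened. The documents do not support that. Section 1.3 refers back to the composition already given, which is water and xylitol, and names no method or agent. On the text, the named ingredient at issue is xylitol alone.

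A third reply is that other safeguards exist. Medical history is verified at the first visit, adverse events are monitored in both phases with telephone calls at days 15 and 75, the principal investigator may unblind when an adverse event is assessed, and the trial is bound to GCP and ISO 14155. A careful investigator would probably not enrol someone with a known intolerance. These lower the likely consequence. But none makes a documented contraindication to the placebo an exclusion, and most of them act only after exposure.

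**Conclusion.** The point holds as a minor correction to eligibility wording, for patient safety. The written exclusion is narrower than the exposure that the crossover plans. Unless every placebo component is also in Hydral, which the documents do not state, a patient with a documented contraindication to a placebo component meets the criteria and could be exposed.

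The size is probably small. Xylitol is the only named placebo ingredient besides water. The documents give no frequency for a contraindication to it, and zero affected patients among 40 is plausible.

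A reader might also infer a bias in Hydral's favour, on the argument that reactions or dropout would fall only in placebo periods. The documents do not support this:

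- Group B takes placebo first, so a Group B patient who leaves in Phase A also loses the Hydral period.
- A patient who leaves early may give no end-of-period placebo score, so dropout does not in itself worsen placebo scores.
- Nothing says that a contraindication to xylitol would change dryness ratings.
- The primary objective in 2.4.1 is descriptive.

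Nor does it help to say that one affected patient is 1/40 = 2.5 percentage points. That is true of any single patient for any reason, and is not evidence of an effect here. No consequence for the efficacy result, the sample size or the analysis has been shown.

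**What to change.** Extend the first exclusion criterion in 2.1 so that it reads: *documented contraindication to any of the components of GUM Hydral or of the placebo (excipients included)*. If the placebo's biological stabilization adds any ingredient, name it in 1.3 so that sites can apply the criterion. If it adds none, a statement that water and xylitol are the complete formula serves the same purpose.

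The scope of the stopping provision in 2.2 should also be reconciled with the planned placebo exposure in 1.5 and 2.3. What that provision should say is for the sponsor and the investigator to settle.

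The cost is one phrase in 2.1 and at most one line in 1.3, which the funder can supply as manufacturer of the placebo. Any effect on recruitment should be negligible, and the design and analysis do not change.

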2.2 WITHDRAWAL PROCEDURES

The intervention will be stopped in any case of reported adverse event that can be attributed to GUM Hydral, or in case the patients will need a drug or a medication which could interfere with the xerostomia symptoms.

In order to improve the adherence of the patients to the protocol interventions, all the patients will be asked to update a diary card reporting the usage of the product.

During the duration of the treatment, the patients will be asked not to use any product analogue of Hydral.

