2.4 STUDY OBJECTIVES

The measurement of xerostomia is problematic. In contrast to hyposalivation, which can be objectively evaluated by using sialometry, xerostomia is comprised of a set of symptoms, and therefore can be assessed only by directly questioning individuals.

The questionnaire which will be used to this evaluation are Xerostomia Questionnaire (13) (14). To the XQ questionnaire, 1 further question was added from Xerostomia Inventory (XI) scale score (15).

The QLQ-C30 provides 30 questions, globally assessing patients' quality of life. The QLQ-H&N35 includes 35 questions, and addresses symptoms associated with specific tumor location, side effects associated with the oncologic treatment and additional QoL aspects modified by the disease or its treatment. The answers will be converted into a linear scoring scale, with values between 0 and 100, (16) (17) as per advocated by EORTC.

The modified XQ provides a measure of the severity of radiation -induced xerostomia that affects the patients' QoL. This questionnaire consists of 10 questions, associated with patient-reported dryness. Moreover, a general question "how dry is your mouth?" has been added to the questionnaire. The modified XQ is a self-administered tool and patients will be asked to rate each symptom on a 10-point NRS scale of 0-10, with higher scores indicating more severe dryness or discomfort due to dryness. Each item score is added, and the sum is linearly transformed to produce the final summary score ranging from 0 to 100, with higher scores representing higher levels of xerostomia.

Patients' compliance will be evaluated by the use of a diary card, in order to notice the amount of product used.

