2.6 RANDOMIZATION

Patients will be randomized to treatment groups using sequentially numbered, opaque sealed envelopes (SNOSE). (23)

The principal investigator will be encharged of generating the allocation sequence, of enrolling the participants and of assigning the interventions to the participants.

The co-workers who will administrate the therapies and the patients themselves will be blinded about the selected product.

Only in case of assessment of any adverse event, it will be possible for the P.I. to reveal the product used during the therapy.

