2.8.2 DATA ANALYSIS

The sample will be described in its clinical and demographic features using descriptive statistics techniques. Quantitative variables will be described using the following measures: minimum, maximum, range, mean and standard deviation. Qualitative variables will be summarized with absolute and percentage frequency tables. Normality of continuous variables will be checked using Kolmogorov-Smirnov test.

The primary objective will be achieved using descriptive statistics techniques, summarizing questionnaires' results at the planned timepoints. Efficacy will be investigated considering an ANOVA mixed model. Adverse events will be described numerically (absolute frequency by type) and qualitatively. Comparison between the two groups in terms of adverse events will be done with a Chi-square test.

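### The adverse-event stop in 2.2 names GUM Hydral only and 2.6 lets the product be revealed for any event, so the text permits one-sided, unblinding stops without settling how the rule is applied

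*Combined protocol and SAP*

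**What the plan says.** Section 2.2 gives two reasons for stopping. The first is tied to one product: "The intervention will be stopped in any case of reported adverse event that can be attributed to GUM Hydral". The second, need for a drug that could interfere with the symptoms, is neutral between products and is not at issue here.

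Section 2.6 describes the blind. Those giving the therapies are blinded, and "the patients themselves will be blinded about the selected product". The principal investigator is not listed as blinded; that person generates the sequence, enrols and assigns. On breaking the code it says "Only in case of assessment of any adverse event, it will be possible for the P.I. to reveal the product used during the therapy".

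Section 2.3 makes every patient due both products: "The investigational product GUM Hydral and the placebo will be each administered for a 30-days treatment period". For the Day 30 stop the same section uses wording that covers both: "the administration of the products will be stopped".

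Section 2.4 says that xerostomia "can be assessed only by directly questioning individuals". In 2.8.2 the analyses that depend on stopped periods are "Efficacy will be investigated considering an ANOVA mixed model" and "Adverse events will be described numerically (absolute frequency by type) and qualitatively", plus a Chi-square comparison of adverse events between groups. No rule is given for scores collected after a stop.

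**The concern.** A stop rule in a blinded trial should not depend on which product the patient is taking. Here the trigger names the active product, and 2.6 gives the person who holds the sequence permission to look before deciding. Nothing in 2.6 limits that look to cases where the patient's care requires it.

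Three things are at stake if the two rules are followed literally:

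- **The blind.** If only Hydral periods can be stopped for an adverse event, the stop names the product. In a two-product crossover it names the other period's product as well. A group A patient stopped in Phase A who goes on to Phase B would answer those questionnaires knowing that the product is placebo, and the outcome is self-reported.
- **Comparable exposure.** Hydral periods with an event would be cut short while placebo periods with the same event ran on.
- **Patients on placebo.** The placebo is water with xylitol. A patient who reacts to it has no adverse-event stop rule.

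Efficacy and adverse events are secondary objectives, but the descriptive primary objective summarises the same questionnaire scores.

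**Working it through.** **1. How the rule can be applied.** Setting 2.2 beside 2.6 gives two routes.

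- *With the code:* an event occurs, the principal investigator looks up the product, stops if it is Hydral and continues if it is placebo. Stops are one-sided and revealing.
- *Blind:* the event is judged possibly product-related without knowing the product, and product is stopped. The same event leads to the same action on either product, and the stop reveals nothing.

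Section 2.6 permits the first route but does not require it. Section 2.2 does not exclude the second. Neither says whether a stopped patient enters the next period.

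**2. The plan's own figure.** Section 2.8.1 gives N=40 for a 30% difference in proportion improved, alpha 0.05, power 80%. For paired proportions, n = (1.96√ψ + 0.84√(ψ − 0.30²))² / 0.30², where ψ is the discordant proportion. The plan gives no ψ. Assumed values of 0.40, 0.48 and 0.50 give 33, 40 and 42. So 40 is attainable but cannot be verified, and this point does not depend on it. It is used below only as the number of patients.

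**3. Illustration for efficacy.** Assumptions, none from the documents except the 40 patients and the 30-point difference: 60% improve on Hydral (24 of 40) and 30% on placebo (12 of 40); k = 2, 4 or 6 stops. One-sided means k stops on Hydral and none on placebo; equal means k on each. Differences are in percentage points.

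| Stopped patients and handling | k=2 | k=4 | k=6 |
|---|---|---|---|
| X: would not have improved anyway; scores kept | 30.0 | 30.0 | 30.0 |
| X: left out, one-sided: 24/(40−k) − 0.30 | 33.2 | 36.7 | 40.6 |
| X: left out, equal: (24−12)/(40−k) | 31.6 | 33.3 | 35.3 |
| Y: average patients who fall to the placebo rate off product; kept, one-sided or equal: [0.6(40−k) + 0.3k]/40 − 0.30 | 28.5 | 27.0 | 25.5 |
| Y: left out, one-sided or equal: 0.60 − 0.30 | 30.0 | 30.0 | 30.0 |
| Z: average patients counted as not improved, one-sided: 0.6(40−k)/40 − 0.30 | 27.0 | 24.0 | 21.0 |
| Z: the same, equal: 0.3(40−k)/40 | 28.5 | 27.0 | 25.5 |

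The part due to one-sidedness is the one-sided row minus the equal row. In X (left out) it is +1.6, +3.3 and +5.3 points. In Y it is zero. In Z it is −1.5, −3.0 and −4.5 points.

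The part due to the open choice between keeping and leaving out scores is larger: 3.2, 6.7 and 10.6 points in X, and 1.5, 3.0 and 4.5 in Y. Even its direction is not fixed. If two stopped Hydral patients were improvers who stayed improved, keeping them gives 30.0 and leaving them out gives 22/38 − 0.30 = 27.9.

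**4. Illustration for adverse-event counts.** Assumptions: the same true rate L per 30 days on both products, every event attributable, product stopped at the first event on Hydral only, and no product-related event afterwards. Expected counts in 40 patients are 40L on placebo and 40(1 − e^(−L)) on Hydral.

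| L | Placebo | Hydral | Shortfall |
|---|---|---|---|
| 0.1 | 4.0 | 3.8 | 5% |
| 0.2 | 8.0 | 7.3 | 9% |
| 0.5 | 20.0 | 15.7 | 21% |

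The number of patients with at least one event is unaffected.

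**The case against.** The strongest reply is that the product name in 2.2 is loose drafting. The protocol often lets the active product stand for both. The flow-chart row on Medical Device administration covers both phases; Notes 4 and 5 put placebo under it, and Note 6 speaks of the first Medical Device administration, which for group B is placebo. Section 2.1 excludes contraindications to Hydral's components without mentioning the placebo's. On this view the rule would be applied blind to any product reaction. That reading is plausible and cannot be excluded. But 2.3 shows that the authors had neutral wording available, and 2.6 gives the means to apply 2.2 literally. The ambiguity itself stands.

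A second reply is that a stop may mean full withdrawal, as the title of 2.2 suggests. Then a group A patient stopped in Phase A never answers the Phase B questionnaires, and the placebo period is lost as well. This also stands. A reader might infer from 2.2 that stops necessarily unblind both periods and shift the Hydral results alone; the documents do not support that, because both the route and the scope of a stop are left open.

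Third, 2.6 permits unblinding for events on either product whatever 2.2 says, so rewording 2.2 alone would not be enough. That is correct, and the fix covers both sections.

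Fourth, on safety: 2.8.2 also plans a Chi-square comparison, which is unaffected if it counts patients with an event, and 3.3 keeps safety recording open to the End of Study Visit. The shortfall in event counts is small unless events are frequent.

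**Conclusion.** The point holds conditionally. The adverse-event stop in 2.2 names Hydral only, there is no placebo counterpart, and 2.6 allows the product to be revealed for any adverse event. Followed literally with the code, these rules give one-sided, revealing stops and leave patients on placebo without a stop rule. Applied blind, they do not. The text does not settle which, nor whether a stop ends the period or participation.

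The size and direction of any bias are undetermined. The documents give no adverse-event rate, so 2, 4 or 6 stops is an assumption, as are the 60% and 30% improvement rates. The illustration also uses proportions improved, whereas 2.8.2 plans a mixed model. Under those assumptions one-sidedness alone is worth +1.6 to +5.3 points in case X with stopped scores left out, nothing in case Y, and −1.5 to −4.5 points in case Z. A reader might take the 1.5 to 10.6 points between keeping and leaving out scores (cases X and Y) as the effect of the one-sided rule, or conclude that the bias favours Hydral. Neither follows: most of that range comes from the missing rule for post-stop scores, and the sign changes with the case chosen.

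This is a worthwhile correction because it protects the blind and patients on placebo at little cost, not because a known bias has been shown.

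**What to change.** 1. In 2.2, replace 'GUM Hydral' with 'the study product (Hydral or placebo)', and require attribution to be judged without revealing the product. Because the principal investigator holds the sequence, one of the blinded staff should make that judgement.
2. In 2.6, limit revealing the product to cases where the patient's care depends on it.
3. State that a stop ends product for that period only, that the period's Day 30 or Day 90 assessments still take place, and that the patient enters the next period if it is safe.
4. In 2.8.2, state that those scores stay in the main mixed model. A sensitivity analysis without them, and adverse events reported by product with days on product, would complete this.

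The cost is wording in these sections, with no new visit, test or patient. There are two downsides. Some placebo periods that would have run on will now be stopped. Keeping off-product scores may also dilute a true effect: by 1.5 to 4.5 points for 2 to 6 stops under the case Y assumptions, which is the reason for the sensitivity analysis.
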